#### Week 28 to 72 (Optional treatment extension)

The treatment duration may be extended by up to 12 additional months beyond the initially scheduled 6 months of treatment, if clinically indicated and at the discretion of the investigator. Patients will continue to be seen monthly while on extended tofacitinib treatment. Assessments of disease severity will continue to be performed via physical exam and photography, and will be objectively quantified using the SALT and Physician global assessment (PGA). Patient global assessment and patient quality of life assessment will also be completed.

PGA and patient evaluations will be based on similar 100mm visual analog scales with 0 labeled as no scalp hair loss and 100 labeled as complete scalp hair loss. Patients and physicians will place a vertical mark along the horizontal line depending on their assessment of the degree of hair loss present at the time of assessment.

Patient quality of life assessments will be based on changes in the Dermatology Life Quality Index DLQI, which we have previously used for patient evaluation in the AA registry, and the Skindex-29 Questionnaire.

Photography will be performed at all visits.

Optional additional biopsies and blood draws may be obtained at the investigator's discretion and with the subject's permission as indicated by clinical considerations such as variation in the timeline to regrowth from one subject to another, focal apparent resistance to treatment, as well as other potential unpredictable clinical occurrences. Unscheduled biopsies and blood draws will ensure that tissue and blood samples can be obtained at optimal time points to evaluate the changes occurring in response (or lack of response) to treatment. The patient will be given the option to agree to, or decline, the additional biopsies and blood draws.

Adverse events will be assessed at every visit.

#### 8, 16, and 24 weeks after end of treatment (follow-up period off study medication)

All patients will be seen at 8, 16, and 24 weeks after completion of study drug, to determine durability of response or evidence for a delayed effect. Importantly patients who achieved  $\geq 50\%$  regrowth as measured by SALT score (responders) will be seen at 8, 16, and 24 weeks after end of study treatment in order to assess the frequency and timing of relapse or to capture the occurrence of further regrowth.

Relapse will be defined as any recurrence of hair loss in responders (subjects achieving greater than 50% decrease in SALT score from baseline during the first 6 to 18 months of the study) who had achieved stable regrowth without continued loss for at least 2 months; and loss of  $\geq 25\%$  of regrowth in patients who had achieved 50% regrowth during treatment but still had chronic low grade hair loss.

Nonresponders will also be offered the option to continue follow-up in order to assess for delayed response. Efficacy evaluations: SALT, PGA, Patient global assessment and patient quality of life assessment will be performed.

Blood draws for safety parameters will be conducted at 8 weeks after end of treatment if deemed necessary to assess normalization of any previously abnormal values.

Adverse events will be assessed at every visit.

Standardized photographs of the subject's scalp will be taken at every visit; blood draws for safety parameters and immune studies will be done based on the attached table of study procedures. Photographs will be used to support determination of percent hair regrowth. Photography will be performed using a high resolution digital camera with Intellistudio system from Canfield Scientific, Inc., Patients will be positioned using a laser guide, after which photographs of the entire scalp will be taken at standardized locations and at a fixed distance. Close-up photographs may also be taken using an epiluminescent attachment in order to assess for the presence of early regrowth.

#### Unscheduled Visits

An unscheduled visit can occur at any time during the study for instance as prompted by signs of infection or local injection site reactions. A source document must be maintained for these unscheduled visits. The date for the visit and any data generated must be recorded on the

appropriate CRF. At treatment discontinuation/early termination subjects will undergo end of study evaluations per the Schedule of Assessments.

#### Telephone contact/retention

Patients will be contacted on a monthly basis, between the planned study visits at 8, 16, and 24 weeks, in the observational phase of the study to ascertain the occurrence of adverse events as well as to assess the status of hair growth or loss.

Any concerns or questions the patient may have will also be addressed. If deemed necessary, the subject may be asked to come in for an unscheduled visit.

#### Duration of Treatment

After the screening period, subjects will begin tofacitinib 5mg twice-daily and will continue treatment for 6 months. The treatment may be extended by up to 12 additional months if clinically indicated at the discretion of the investigator.

The 18-month treatment period is expected to provide adequate time to assess the short-term efficacy and safety of tofacitinib in patients with moderate to severe AA, AT or AU. Responders will then be followed for 6 months off drug.

#### Study Population

For entry into the study, the following criteria MUST be met. Any exceptions must be approved by the Principal Investigator and/or IRB before enrollment.

## **7.2 Inclusion Criteria**

### **1) Signed Written Informed Consent**

Before any study procedures are performed, subjects will have the details of the study described to them, and they will be given a written informed consent document to read. Subjects will have the opportunity to ask questions. They may also take the Informed Consent document home for discussion with family or friends. If subjects consent to participate in the study, they will indicate that consent by signing and dating the informed consent document in the presence of study personnel. A copy of the signed informed consent will be given to the subject.

- 2) Men and women between the ages of 18 and 65 years of age.
- 3) Patients with a diagnosis of moderate to severe patch type alopecia areata
- 4) Patients with alopecia totalis or universalis may be enrolled
- 5) Patients will have >30% and <95% total scalp hair loss at baseline as measured using the SALT score to qualify as moderate to severe patch type AA; and 95-100% scalp hair loss to qualify as alopecia totalis or universalis
- 6) Duration of hair loss greater than 3 months without an upper limit of duration as long as there is reason to believe that regrowth is possible in the opinion of the investigator.
- 7) No evidence of significant active ongoing regrowth present at baseline.

- 8) Patients with a history of alopecia totalis/universalis can be included as long as the current episode of hair loss meets the criteria of 30 to 95% hair loss (i.e. they are not currently AT or AU), and as long as in the opinion of the investigator there does appear to be potential for regrowth. Patients with current episodes of alopecia totalis/universalis may be included in this study.
- 9) Vaccinations should be up to date in agreement with current immunization guidelines prior to start of tofacitinib. The patient will be asked to obtain verbal verification from their primary care provider that this is the case.
- 10) Patients may be naïve to treatment or unresponsive to intralesional (IL) steroids or other treatments for alopecia areata.
- 11) Women of childbearing potential (WOCBP) must use highly effective methods of birth control [for at least 12 weeks after the last dose of investigational product] to minimize the risk of pregnancy. WOCBP must follow instructions for birth control for the entire duration of the study including a minimum of 90 days after dosing has been completed.

Acceptable methods of highly effective birth control include:

- Condom with spermicide
- Diaphragm and spermicide
- Cervical cap and spermicide

The use of intrauterine devices, (IUDs) shall be at the discretion of the investigator.

- a) Women must have a negative serum or urine pregnancy test (minimum sensitivity 25 IU/L or equivalent units of HCG) within 24 hours prior to the start of investigational product.
- b) Women must not be breastfeeding

## 7.3 Exclusion Criteria

### 1) Sex and Reproductive Status

- a) WOCBP who are **unwilling or unable** to use an acceptable method to avoid pregnancy for the entire study period and for up to 12 weeks after the last dose of study drug.
- b) WOCBP using a prohibited contraceptive method.
- c) Women who are pregnant or breastfeeding.
- d) Women with a positive pregnancy test on enrollment or before administration of tofacitinib.
- e) Sexually active fertile men not using effective birth control if their partners are WOCBP.

### 2) Target Disease Exceptions

- a) Patients with a history of or active skin disease on the scalp such as psoriasis or seborrheic dermatitis.
- b) Patients in whom the diagnosis of alopecia areata is in question or in whom the pattern of hair loss is such that quantification of hair loss and assessment of regrowth is difficult.

E.g. patients with diffuse alopecia areata. This assessment is at the investigator's discretion.

- c) Patients with active medical conditions or malignancies (except adequately treated basal or squamous cell carcinoma) that in the opinion of the investigator would increase the risks associated with study participation, including patients with a history of recurrent infections.
- d) Patients with hemoglobin levels <9 g/dL, lymphocyte count <500 cells/mm^3, absolute neutrophil count (ANC) < 1000 cells/mm^3, at baseline.
- e) Patients known to be HIV or hepatitis B or C positive.
- f) Patients with history or evidence of moderate or severe hepatic and/or renal impairment.
- g) Patients with history of immunosuppression or history of recurrent serious infections.

### 3) Coexisting disease or concurrent medications

- a) Patients taking potent inhibitors of Cytochrome P450 3A4 (e.g. ketoconazole)
- b) Patients receiving one or more concomitant medications that result in both moderate inhibition of CYP3A4 and potent inhibition of CYP2C19 (e.g., fluconazole).
- c) Patients known to be HIV or hepatitis B or C positive.
- d) Patients with evidence of infection or active/untreated skin cancer.
- e) Patients who have been treated with intralesional steroids, systemic steroids, anthralin, squaric acid, DPCP (diphenylcycloprophenone), protopic, minoxidil or other medication which in the opinion of the investigator may affect hair regrowth within one month of the baseline visit.
- f) Patients who are impaired, incapacitated, or incapable of completing study-related assessments.
- g) Patients with current symptoms of severe, progressive, or uncontrolled renal, hepatic, hematologic, gastrointestinal, pulmonary, cardiac, neurologic, or cerebral disease, which, in the opinion of the investigator, might place a subject at unacceptable risk for participation in the study.
- h) Female patients who have had a breast cancer screening that is suspicious for malignancy and in whom the possibility of malignancy cannot be reasonably excluded by additional clinical, laboratory, or other diagnostic evaluations.
- i) Patients with a history of cancer in the last 5 years, other than non-melanoma skin cell cancers cured by local resection or carcinoma in situ. Existing non-melanoma skin cell cancers should be removed, the lesion site healed, and residual cancer ruled out before administration of the study drug.
- j) Patients who currently abuse drugs or alcohol.
- k) Patients with evidence (as assessed by the investigator) of active or latent bacterial or viral infections at the time of potential enrollment, including subjects with evidence of human immunodeficiency virus (HIV) detected during screening.
- l) Patients with herpes zoster or cytomegalovirus (CMV) that resolved less than 2 months before the informed consent document was signed.

- m) Patients who have received any live vaccines within 3 months of the anticipated first dose of study medication. Subjects may not receive live vaccine concurrently with tofacitinib.
- n) Patients with a history or symptoms suggestive of gastrointestinal perforation or disorders that might increase the risk of GI perforation such as gastric ulcers or diverticulitis
- o) Patients who take NSAIDs at high dose or on a frequent basis, which in the investigator's opinion might increase the risks of gastrointestinal perforation
- p) Patients with any serious bacterial infection within the last 3 months, unless treated and resolved with antibiotics, or any chronic bacterial infection (e.g., chronic pyelonephritis, osteomyelitis, or bronchiectasis).
- q) Patients at risk for tuberculosis (TB). Specifically excluded from this study will be subjects with a history of active TB within the last 3 years, even if it was treated; a history of active TB greater than 3 years ago, unless there is documentation that the prior anti-TB treatment was appropriate in duration and type; current clinical, radiographic, or laboratory evidence of active TB; and latent TB that was not successfully treated ( $\geq 4$  weeks).

#### 4) Physical and Laboratory Test Findings

- a) Patients must not be positive for HIV, Hepatitis B or C.
- b) Patients who are positive for hepatitis C antibody if the presence of hepatitis C virus was also shown with polymerase chain reaction or recombinant immunoblot assay.
- c) Patients with any of the following laboratory values
  - i) Hemoglobin  $<9.0$  g/dL
  - ii) Lymphocytes  $<500/\text{mm}^3$
  - iii) ANC  $<1000 \text{ cells/mm}^3$
  - iv) Serum creatinine  $>2$  times the ULN
  - v) Serum ALT or AST  $>2$  times the ULN

Any other laboratory test results that, in the opinion of the investigator, might place a subject at unacceptable risk for participation in the study.

#### 7.4 Prohibited Treatments and/or Therapies

- a) Patients who have at any time received treatment with any investigational drug within 28 days (or less than 5 terminal half-lives of elimination) of the Day 1 dose.
- b) Any concomitant Disease Modifying Anti-Rheumatic Drugs (DMARDs) or immunosuppressants, such as anakinra, methotrexate, adalimumab, etanercept, azathioprine, cyclosporine, corticosteroids, etc.
- c) Patients who have been treated with intralesional steroids, systemic steroids, anthralin, squaric acid, DPCP (diphenylcycloprophenone), protopic, minoxidil or other medication which in the opinion of the investigator may affect hair regrowth within one month of the baseline visit.

- d) Patients receiving potent inhibitors of Cytochrome P450 3A4 (CYP3A4) (e.g., ketoconazole)
- e) Patients receiving one or more concomitant medications that result in both moderate inhibition of CYP3A4 and potent inhibition of CYP2C19 (e.g., fluconazole).

Eligibility criteria for this study have been carefully considered to ensure the safety of the study patients and to ensure that the results of the study can be used. It is imperative that patients fully meet all eligibility criteria.

## **7.5 Women of Childbearing Potential**

Women of childbearing potential (WOCBP) include any female who has experienced menarche and who has not undergone successful surgical sterilization (hysterectomy, bilateral tubal ligation, or bilateral oophorectomy), and who is not postmenopausal. Post menopause is defined as:

- Amenorrhea  $\geq$  12 consecutive months without another cause, and a documented serum follicle stimulating hormone (FSH) level  $> 35$  mIU/mL or
- Women with irregular menstrual periods and a documented serum follicle stimulating hormone (FSH) level  $> 35$  mIU/mL or

NOTE: FSH level testing is not required for women  $\geq$  62 years old with amenorrhea of  $\geq$  1 year

- Women on hormone replacement therapy (HRT)

Women who are using oral or other hormonal contraceptives, such as vaginal products, skin patches, or implanted or injectable products, or mechanical products, such as an intrauterine device or barrier methods (diaphragm, condoms, spermicides), to prevent pregnancy or who are practicing abstinence or who have a sterile (e.g., vasectomy) partner should be considered to be of childbearing potential.

## **7.6 Concomitant Treatments**

### **7.6.1 Prohibited and/or Restricted Treatments**

Any medication known to affect hair growth in alopecia areata including but not limited to topical, intralesional or systemic steroids, squaric acid, anthralin, protopic, minoxidil, diphenylcyclopropenone, cyclosporine and any other medications, which in the judgment of the investigator, may affect hair growth in patients with alopecia areata.

Any medications known to be potent inhibitors of cytochrome P450 3A4 (CYP3A4) (e.g., ketoconazole), or one or more concomitant medications that result in both moderate inhibition of CYP3A4 and potent inhibition of CYP2C19 (e.g., fluconazole), due to loss or reduced clinical response to tofacitinib.

Any immunosuppressive drugs (e.g., azathioprine, tacrolimus, cyclosporine), that can potentiate risk for immunosuppression.

### **7.6.2 Other Restrictions and Precautions**

Not applicable.

## **7.7 Discontinuation of Subjects from Treatment**

Subjects MUST discontinue study treatment and withdraw from the study for any of the following reasons:

- Withdrawal of informed consent (subject's decision to withdraw for any reason)
- Any clinical adverse event (AE), laboratory abnormality, or intercurrent illness which, in the opinion of the investigator, indicates that continued participation in the study is not in the best interest of the subject
- Pregnancy
  - Instruct WOCBP to contact the investigator or study staff immediately if they suspect they might be pregnant (e.g., missed or late menstrual period) at any time during study participation. Institutional policy and local regulations should determine the frequency of on-study pregnancy tests for WOCBP enrolled in the study.
- Loss of ability to freely provide consent through imprisonment or involuntarily incarceration for treatment of either a psychiatric or physical (e.g., infectious disease) illness.

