#### *Secondary efficacy outcomes in detail*

1. Percent hair regrowth from baseline determined by SALT measurements following end of treatment (at 24 to 72 weeks) and during the observational phase at 8, 16, and 24 weeks after end of treatment.

2. Comparison of the proportion of responders in the experimental group with the historically known placebo response rate (<10%), with response defined as 50% change in SALT score (50% regrowth) from baseline, at end of treatment (week 24 to 72), and at the end of study (8, 16, and 24 weeks after end of treatment).
3. Comparison of the proportion of subjects in each group attaining global overall improvement SALT score of A5 (100% coverage) supported by ≤ SALT 25 at the end of treatment (week 24 to 72), and at the end of study (8, 16, and 24 weeks after end of treatment).
4. Change in PGA (Physician Global Assessment) based on live evaluations and evaluation of standardized photographs between baseline, and each subsequent visit during the treatment period and the follow up period.
5. Change in patient global assessment between baseline, and each subsequent visit during the treatment period and the follow up period.
6. Change in patient quality of life assessment from baseline compared to subsequent visits during the treatment period and the follow up period.
7. Frequency of occurrence and timing of relapse (as defined above) in responders followed for 6 months off therapy.
8. Safety will be evaluated as a secondary endpoint using descriptive statistics to summarize the cumulative incidence and types of AEs.
9. The proportion of patients who discontinued treatment will be summarized.

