### **8.2.1 Dose Modifications for Adverse Events**

If there is evidence of toxicity, as determined by laboratory tests or by clinical assessment that could place the subject at increased risk in the judgment of the investigator, administration of tofacitinib will be decreased or interrupted. Subjects may be considered eligible to continue with tofacitinib treatment only if full resolution of the adverse event is documented.

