## **12.6 Nonserious Adverse Events**

The investigator will begin collecting nonserious adverse event (NSAE) information once administration of the investigational product is initiated.

All identified NSAEs must be recorded and described in the medical record. If an ongoing NSAE worsens in its intensity, or if its relationship to the investigational product changes, a new NSAE entry for the event should be completed. NSAEs should be followed to resolution or stabilization, or reported as SAEs if they become serious. Follow-up is also required for NSAEs that cause interruption or discontinuation of investigational product, or those that are present at the end of study participation. Subjects with NSAEs at study completion should receive post-treatment follow-up as appropriate.

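### Section 7.7 joins permanent drug discontinuation to study withdrawal, which cuts short off-drug follow-up and makes relapse and durability data missing for reasons tied to toxicity

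*Combined protocol and SAP*

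**What the plan says.** Section 7.7 is headed as discontinuation from treatment, but its instruction goes further: "Subjects MUST discontinue study treatment and withdraw from the study for any of the following reasons". Four reasons follow: withdrawal of consent; an adverse event, laboratory abnormality or intercurrent illness; pregnancy; and loss of the ability to consent freely. The second is qualified. It applies to an event "which, in the opinion of the investigator, indicates that continued participation in the study is not in the best interest of the subject". Toxicity short of that falls under 8.2.1, where "administration of tofacitinib will be decreased or interrupted" and the subject may continue once the event has fully resolved.

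At the stop, 7.1 (Unscheduled Visits) says: "At treatment discontinuation/early termination subjects will undergo end of study evaluations per the Schedule of Assessments". Section 9.1 (Early Termination) lists the content: adverse event review, photography, SALT, physician and patient global assessments, quality of life, and laboratory tests if indicated. Section 12.5 collects serious adverse events for 30 days after the last dose. Section 12.6 adds: "Follow-up is also required for NSAEs that cause interruption or discontinuation of investigational product".

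Off-drug follow-up is described in 7.1: "All patients will be seen at 8, 16, and 24 weeks after completion of study drug, to determine durability of response" or a delayed effect. Monthly calls fall between those visits. Section 11.1.1 follows responders for 6 months or until relapse and does not require nonresponders to attend. The listed secondary outcomes (5.2, 11.1.1, 13.3) include response status at 8, 16 and 24 weeks off drug and "Frequency of occurrence and timing of relapse (as defined above) in responders followed for 6 months off therapy".

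**The concern.** The protocol defines no status of being off drug but still followed. An investigator who decides under 7.7 that a subject should permanently stop because of toxicity has no written route to keep that subject under observation. The subjects who then drop out of the off-drug phase are selected by toxicity, so the loss cannot be assumed unrelated to what happens afterwards.

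Two things are at stake. One is the relapse and durability outcome, which can be observed only after the drug is stopped. The other is routine adverse event review out to 24 weeks off drug. The plan has no rule to fall back on: 13.2 (Populations for Analyses) contains only accrual text, and section 13 gives no missing-data rule beyond summarising the proportion who discontinued.

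**Working it through.** The plan states no figure on this point, so the main check sets the sections side by side.

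**1. What 7.7 takes away.** Followed literally, a subject who has left the study has the early-termination evaluation and then none of the scheduled off-drug visits or calls in 7.1 and 9.1.

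**2. What remains.** The early-termination evaluation (including SALT), 30-day serious adverse event collection (12.5), follow-up of the event that caused the stop (12.6), and discretionary extra laboratory tests after end of treatment (Table 3 footnote).

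**3. Where the sections do not fit together.**
- 7.1 says "All patients will be seen at 8, 16, and 24 weeks after completion of study drug". It does not say whether a subject stopped for an adverse event has completed study drug. Section 11.1.1 likewise does not say whether a responder stopped for toxicity stays in follow-up.
- 12.9.2 requires both discontinuation and follow-up procedures after a pregnancy, unless pregnancy contraindicates them. Section 7.7 requires withdrawal from the study.
- 12.6 requires follow-up of the causal event but attaches no visits to it.
- Sections 10 and 13.4.2 report serious adverse events through the follow-up visits, while 12.5 sets 30 days. For a withdrawn subject there are no follow-up visits, so the longer window has nothing to run on.
- 9.2 and 9.2.1 record early withdrawal and drug discontinuation separately, so the protocol elsewhere treats them as different events.

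**4. Timing of recovery.** Section 2.3.4 puts the return of creatinine to baseline at four to six weeks after discontinuation. Section 4 says natural killer cell changes generally resolved in 2 to 6 weeks. An evaluation made when the drug is stopped precedes both. The protocol's own check for normalisation of abnormal values, done if deemed necessary, is placed 8 weeks off drug, at a visit that 7.7 ends.

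**5. Follow-up lost per subject.** 24 weeks / 52.18 weeks per year = 0.46 patient-years. This is an upper limit, because responders are followed only until relapse.

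**6. Effect on the relapse rate (illustration on assumed counts).** Take 7 responders, since 48% of 15 is 7.2 and 48% is the response rate in 13.1. Assume 3 relapses among those still followed, and k responders lost through 7.7.
- Observed rate = 3/(7 - k).
- Lower bound, if no lost responder relapses = 3/7.
- Upper bound, if every lost responder relapses = (3 + k)/7.

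| k lost | Observed rate | Possible range for all 7 |
|---|---|---|
| 0 | 3/7 = 43% | 43% |
| 1 | 3/6 = 50% | 3/7 to 4/7 = 43-57% |
| 2 | 3/5 = 60% | 3/7 to 5/7 = 43-71% |
| 3 | 3/4 = 75% | 3/7 to 6/7 = 43-86% |

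These ranges reflect missing data only. Sampling error is additional: with nobody lost, the exact 95% interval for 3/7 is already 10% to 82%.

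**The case against.** The strongest reply is that 7.7 bites less often, and costs less, than it first appears. Much of that stands.

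- **Trigger.** A reader might infer that anyone who stops drug for an adverse event must leave. The documents do not say so: the trigger is the investigator's judgement about continued participation, and other toxicity leads to dose decrease or interruption.
- **Safety data.** A reader might infer that off-drug safety data disappear and that resolution of toxicity is seen only in those who tolerated the drug. Sections 12.5 and 12.6 contradict this. What is lost is scheduled review, not follow-up of the causal event.
- **Pregnancy.** Section 12.9.2 already provides follow-up. The problem is that 7.7 is not squared with it.
- **Cancelled visits.** No sentence expressly cancels the off-drug visits, and 7.1 speaks of all patients. The loss follows from the plain meaning of withdrawing from the study, so at the least the sections are unreconciled.
- **Primary endpoint.** A reader might infer damage here too. The early-termination visit records SALT, so response at the end of treatment is captured. How to classify a stop before week 24 is a separate question.
- **Size.** One might assume 1 to 3 withdrawals and quote 1/15 to 3/15, or 7% to 20%, of off-drug follow-up lost. That count has no source in the documents. The denominator is also wrong: nonresponders need not attend and responders stop at relapse, so the 15 subjects do not each owe 24 weeks.

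The reply does not remove the central defect. When the 7.7 judgement is made, permanent stop and study exit are one mandatory act, and the off-drug outcomes of those subjects are not scheduled to be collected.

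**Conclusion.** The point holds as a coupling of two decisions that should be separate, and as an inconsistency with 7.1, 11.1.1 and 12.9.2. It truncates off-drug safety data and puts listed secondary outcomes at risk of missingness related to toxicity. That withdrawn subjects would in fact relapse differently is a reasonable inference, but the documents give no evidence on it.

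The size cannot be stated, because no withdrawal rate is given. Per withdrawn responder the loss is at most 0.46 patient-years. The 43-57% to 43-86% ranges rest on assumed counts of 7 responders, 3 observed relapses and 1 to 3 losses; they show only that with so few responders each loss matters. The efficacy analyses are descriptive and meant to inform later trials (13.4.3), so the change is a worthwhile, inexpensive improvement and does not bear on whether the primary analysis can be done.

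**What to change.** Leave the reasons for stopping treatment, and the investigator's judgement, as they are, and change only what follows for study participation.

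1. In 7.7, separate stopping treatment from leaving the study. Limit mandatory study withdrawal to withdrawal of consent or loss of the ability to consent.
2. Reword the adverse event bullet so that it refers to continued treatment. It is now written in terms of study participation, so deleting the withdrawal phrase alone would keep in the study a subject whose participation had just been judged not in their interest.
3. State in 7.1 and 11.1.1 that other subjects who stop early are asked to attend the existing 8, 16 and 24-week visits on the same terms as completers: responders to 6 months or relapse, nonresponders optional.
4. Reconcile 7.7 with 12.6 and 12.9.2, and the serious adverse event window in 12.5 with sections 10 and 13.4.2.
5. State in section 13 that these subjects are counted in the responder and relapse summaries. For any responder still lost, report the lower and upper bounds as in the table above.

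The cost is protocol wording and, for each such subject, at most three visits that are already in the schedule. Subjects remain free to withdraw consent, so some loss may persist.
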